I confirm that I have finished exploring the Decision Support Tool.

- Yes, I am ready to continue

Below is the link to the last section to explore, the Information Center. It will open in a new window. When you are done exploring, return back here and click 'Next Page.'

Please click the link below and use the following access code: [record-name]

[Click Here \(Link 3 of 3\): Information Center](#)

0%

15%

100%

I confirm that I have finished exploring the three links provided and I am ready to continue the survey.

Yes, I am ready to continue

(If not, please finish exploring the three links; they are provided at the bottom of this page)

Keep in mind, you can revisit any of the sections at any time while completing the survey (your access code: [record-name])

Guide

Decision Support Tool

Information Center

0%

18%

100%

If you were a patient diagnosed with DCIS, what treatment option would you choose?

- Active monitoring
- Lumpectomy
- Lumpectomy with radiation
- Mastectomy

0%

21%

100%

Why did you choose this treatment option? (You may list several reasons)

Please rate, how confident are you in your treatment choice?

- 1 Not at all confident
- 2
- 3
- 4
- 5 Very confident

0%

24%

100%

How comfortable would you be with active monitoring as your initial treatment for DCIS?

- 1 Not at all comfortable
- 2
- 3
- 4
- 5 Very comfortable

How comfortable would you be with lumpectomy as your initial treatment for DCIS?

1 Not at all comfortable
 2
 3
 4
 5 Very comfortable

How comfortable would you be with lumpectomy with radiation as your initial treatment for DCIS?

1 Not at all comfortable
 2
 3
 4
 5 Very comfortable

How comfortable would you be with mastectomy as your initial treatment for DCIS?

1 Not at all comfortable
 2
 3
 4
 5 Very comfortable

If you choose active monitoring as your treatment, how likely is it that your DCIS will progress to invasive cancer within 10 years after diagnosis?

1 Not at all likely
 2
 3
 4
 5 Very likely

Please note: for the rest of the survey when we use the term 'DCIS website', we are referring to the collection of all three links you reviewed (Guide, Decision Support Tool, and Information Center).

After you have reviewed the DCIS website, how much do you know about ductal carcinoma in situ, abbreviated as DCIS?

1 I know very little about DCIS
 2
 3
 4
 5 I know a lot about DCIS

What do you think about the amount of information on the DCIS website?

1 Too little information was provided
 2
 3

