 4 The amount of information was just right
 5
 6
 7 Too much information was provided

How clear was the information on the DCIS website?

1 Not at all clear
 2
 3
 4 Somewhat clear
 5
 6
 7 Extremely clear

How helpful was the information on the DCIS website for making a decision about DCIS treatment?

- 1 Not at all helpful
- 2
- 3
- 4 Somewhat helpful
- 5
- 6
- 7 Extremely helpful

Would you recommend the DCIS website to a friend diagnosed with DCIS?

- 1 No
- 2
- 3
- 4 Not sure
- 5
- 6
- 7 Yes

0% 33% 100%

How likely might a breast biopsy miss invasive cancer?

- A biopsy will always show correctly if there is invasive cancer
- There is about a 1-5 % chance that biopsy misses invasive cancer
- There is about a 6-10 % chance that biopsy misses invasive cancer
- There is about an 11-15 % chance that biopsy misses invasive cancer
- There is a more than 15% chance that biopsy misses invasive cancer

Is DCIS the same as invasive breast cancer?

- Yes
- No

The following options are used to treat DCIS patients (choose all that apply):

- Active monitoring
- Endocrine therapy
- Lumpectomy
- Mastectomy
- Chemotherapy
- Radiation

0% 36% 100%

For a woman diagnosed with DCIS, how much does waiting 3-4 weeks to make a treatment decision affect her chances of survival?

- A lot
- Somewhat
- A little or not at all

With active monitoring, about how many women diagnosed with DCIS do you think will die of breast cancer in 10 years?

- Most will die of breast cancer
- About half will die of breast cancer
- Most will NOT die of breast cancer

After which treatment is it more likely that women will need to have a second surgery to remove leftover tumor cells?

- Lumpectomy
- Mastectomy without reconstruction
- Equally likely for both

Which treatment option does NOT affect the appearance of the breast?

- Active monitoring
- Lumpectomy
- Lumpectomy with radiation
- Mastectomy

On average, which DCIS patients do you think have the highest chance of being diagnosed with invasive cancer in the same breast, within 10 years of diagnosis?

- Women who choose active monitoring
- Women who choose a mastectomy
- Women who choose a lumpectomy with radiation
- There is no difference between the above options

After a lumpectomy, what is the traditional schedule for radiation treatment?

[figure not shown]
- 1 day a week for 5 to 6 weeks
- 3 days a week for 6 weeks
- 5 days a week for 3 weeks
- 5 days a week for up to 10 weeks

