H1: Participants who receive in-depth AM information are more likely to choose AM post-tool compared to participants in the control group.

Secondary Outcome 1: Post-tool acceptability of the different treatment options. Measured as categorical 5-point Likert scale from “Not at all comfortable” (1) to “Very comfortable” (5); analyzed as continuous variable. The following question is repeated four times, each time substituting OPTION X for one of the four treatment options:

- Q2.1: How comfortable would you be with **OPTION X** as your initial treatment for DCIS?

H2.1: Participants who receive in-depth AM information report higher AM acceptability compared to participants in the control group.

Secondary Outcome 2: Subjective perception of active monitoring riskiness. Measured as categorical 5-point Likert scale from “Not at all likely” (1) to “Very likely” (5); analyzed as continuous variable.

Q2.2: If you choose active monitoring as your treatment, how likely is it that your DCIS will progress to invasive cancer within 10 years after diagnosis?

- (1) Not at all likely
- (2)
- (3)
- (4)
- (5) Very likely

H2.2: Participants who receive in-depth AM information perceive AM to be subjectively less risky than participants in the control group.

Secondary Outcome 3: Post-tool mastectomy choice. Presented to participants as a categorical item: active monitoring, lumpectomy, lumpectomy with radiation, mastectomy. Recorded for analysis as binary: mastectomy vs non-mastectomy.

Q2.3: see Q1

H2.3: Participants who receive in-depth AM information are less likely to choose a mastectomy compared to participants in the control group.

Secondary Outcome 4: Change in self-perceived knowledge about DCIS. Measured pre- and post-tool as a categorical 5-point Likert scale from “I know very little about DCIS” (1) to “I know a lot about DCIS” (5); analyzed as continuous variable.

Q2.4: How much do you know about ductal carcinoma in situ, abbreviated as DCIS?

- (1) I know very little about DCIS
- (2)
- (3)
- (4)
- (5) I know a lot about DCIS

H2.4: In both groups, self-perceived knowledge about DCIS is higher post-tool compared to pre-tool.

H. Exploratory Aims

See next sections for details about covariates and additional scales used in the explanatory aims.

Exploratory Aim1: Descriptive analyses of the following scales:

- a) DCIS knowledge (11 questions), including AM knowledge (2 questions)
- b) Choice confidence (1 question)
- c) Information needs satisfaction

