 - Measured as categorical 5-point Likert scale from "Not at all confident" (1) to "Very confident" (5); analyzed as continuous variable
- Medical Maximizer Minimizer Scale (Scherer et al., 2020) (MM1; post-tool)
 - Measured as categorical 6-point Likert scale from "I strongly lean toward waiting and seeing" (1) to "I strongly lean toward taking action" (6); analyzed as continuous variable
- Self-reported breast cancer knowledge (pre-tool)
 - Measured as 5-point Likert scale from "I know very little about breast cancer" (1) to "I know a lot about breast cancer" (5); analyzed as continuous variable
- Information Needs Satisfaction (Adapted from Hess, 2012) (post-tool)
 - Measured as 4-item scale, each item elicited on a 7-point Likert scale; items analyzed separately as continuous variables
- Knowledge Scale (De novo)
- Knowledge Scale: Decision Quality Instrument (Adapted from Sepucha, et al., 2019)
- Preparation for Decision Making (PDMS) (Bennett, et al., 2010) (post-tool)
 - Measured as 9-item scale, each item elicited on a 5-point Likert scale from "Not at all" (1) to "A great deal" (5); for each participant, the average score across 9 items is recorded and analyzed as a continuous variable.
- Usability Question (open text field)
- Treatment Choice Reason (open text field)
- Aspects of Health Literacy Scale (AAHLS) (Chinn et al., 2013)
- Personality Scales
 - Attitude Toward Risk (Zhang et al., 2019)
 - Pain Tolerance (McCracken et al., 1992; two questions from each subscale)

- Importance of Appearance (Borzekowski et al., 2000)
- Cancer Fear (Lerman Worry Scale, 1991)

K. Statistical Analysis

K.1. Descriptive statistics

We will describe demographic characteristics and pre-tool general knowledge for the full sample, as well as by study arm (Table 1), using proportions for categorical variables and means with standard deviations or medians with quartiles for continuous variables. Group differences will be evaluated using chi-square tests for categorical variables and Kruskal-Wallis tests for continuous variables. We will also describe the proportion of responses on the primary outcome of treatment choice, and the means and proportions for the secondary outcomes by study arm (Table 2).

K.2. Primary outcome analysis

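### The amount-of-information item is best at its midpoint, so analysing it as a continuous score shows the net lean between too little and too much, not satisfaction

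*SAP*

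**What the plan says.** SAP section J describes the Information Needs Satisfaction scale as "Measured as 4-item scale, each item elicited on a 7-point Likert scale; items analyzed separately as continuous variables". Section H lists it among the scales to be described under Exploratory Aim 1 ("c) Information needs satisfaction"). Section K.4 leaves the methods for Exploratory Aims 1 to 4 ad hoc.

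The items are printed in Protocol Appendix 1. It has exactly four items on a 7-point scale, asked one after another: amount, clarity, helpfulness and recommendation. The first asks "What do you think about the amount of information on the DCIS website", and its labelled points are:

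- "1 Too little information was provided"
- "4 The amount of information was just right"
- "7 Too much information was provided"

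The clarity item ends at "7 Extremely clear" and the helpfulness item at "7 Extremely helpful". The recommendation item runs from no (1) to yes (7). Neither document gives a recode or a separate rule for the amount item.

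**The concern.** On three of the four items a higher score is a better score. On the amount item both ends are complaints and the middle is the ideal. Treating it as continuous in the same way has two consequences.

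- Answers below 4 offset answers above 4. A divided group and a contented group can have the same mean.
- Scores of 3 and 5 are equally far from ideal but sit two points apart. A move from one to the other registers as a change of 2 with no change in how well the amount suited the reader.

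The item is reported under a satisfaction label beside three items where up means better, so its mean is easy to misread. If it were also entered in the Exploratory Aim 5 model as a single linear term, too little and too much would be forced to have opposite associations with treatment choice.

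At stake is one exploratory description of the tool. No hypothesis in section G, no row named in SAP Tables 2 or 3, and no part of the sample size depends on it.

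**Working it through.** **Inputs.** The scale anchors come from Protocol Appendix 1, the coding rule from SAP section J, and n = 101 per arm from SAP section E. The documents give no expected responses, SD or effect size for this item, so there is no stated figure to reproduce. The response counts below are assumptions, chosen to show what the mean can and cannot distinguish.

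**Formulas.** With counts c(s) for scores s = 1 to 7 and n = 101: mean = Σ s·c(s)/n; share just right = c(4)/n; mean distance from ideal = Σ |s − 4|·c(s)/n.

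| Group (assumed) | Counts, scores 1 to 7 | Mean | SD | Too little / just right / too much | Mean distance from 4 |
|---|---|---|---|---|---|
| D, mostly just right | 0, 3, 10, 75, 10, 3, 0 | 4.00 | 0.66 | 12.9% / 74.3% / 12.9% | 32/101 = 0.32 |
| E, divided | 15, 15, 10, 21, 10, 15, 15 | 4.00 | 2.03 | 39.6% / 20.8% / 39.6% | 170/101 = 1.68 |
| F, leaning to too much | 0, 2, 5, 40, 24, 20, 10 | 489/101 = 4.84 | 1.16 | 6.9% / 39.6% / 53.5% | 103/101 = 1.02 |
| F reversed, leaning to too little | 10, 20, 24, 40, 5, 2, 0 | 8 − 4.84 = 3.16 | 1.16 | 53.5% / 39.6% / 6.9% | 103/101 = 1.02 |

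**Cancellation (D against E).** The means differ by 4.00 − 4.00 = 0. Both distributions are symmetric about 4, so the Welch test and the Kruskal-Wallis test each give p = 1.0, and both medians are 4. Yet the share just right is 75/101 = 74.3% against 21/101 = 20.8%, a gap of 53.5 points. Only the spread shows the difference.

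**Direction (three pairs).**

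- D to F: the mean rises by 4.84 − 4.00 = 0.84 and just right falls from 74.3% to 39.6%, a loss of 34.7 points.
- F reversed to D: the mean rises by 4.00 − 3.16 = 0.84 and just right rises from 39.6% to 74.3%, a gain of 34.7 points.
- F reversed to F: the mean rises by 4.84 − 3.16 = 1.68 and just right does not change.

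The same difference in means can therefore go with a worse, a better or an unchanged result, depending on which side of 4 the groups lie.

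**Three categories.** The category column separates all four groups. It ranks D above both F and E on just right, and it shows which way F and its reverse lean. Distance from 4 also ranks them, but it gives F and its reverse the same value (1.02), so the direction is lost.

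**Aim 5.** Suppose the item entered model (1) linearly with coefficient γ on the log scale. Relative to a score of 4, a score of 3 would carry exp(−γ) and a score of 5 exp(+γ). A symmetric U-shaped association would give γ near 0 and be missed.

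Whether the item enters is unclear. Section H words Aim 5 in terms of covariates and personality scales, and section J lists this scale outside its personality group. Section K.4 refers to the additional scales of sections I and J without that limit.

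**The case against.** The strongest reply is that little depends on this item. It is exploratory and descriptive, its methods are left ad hoc, and no between-arm comparison of it is specified. The mean (SD) or median (quartiles) wording in K.1 is written for demographics and pre-tool knowledge. Because the items are analysed separately, this one cannot distort a summed satisfaction score. The raw mean is a valid measure of net lean, a reported SD would hint at a divided group (0.66 against 2.03 above), and a reader who looks at the labels would not take 4.84 for a good score. All of that stands, and it limits the point to exploratory reporting. It does not remove the point: section J does fix the coding, and for this item that coding does not measure the construct named.

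Three stronger readings are tempting, and the documents support none of them.

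- *The error favours the intervention.* SAP section D gives the intervention tool in-depth content on four options and the control tool on three, so a reader might expect more too-much answers in the intervention arm. That is conjecture. Control participants are also offered active monitoring in the choice question, without in-depth content on it. They might answer too little, in which case a higher intervention mean would be a real improvement.
- *The plan will make a worse tool look better.* That happens only if higher is read as better on this item, and the plan does not say so.
- *The Aim 5 model is misspecified.* The item may not enter that model. If it does, the association could be monotone, and then a linear term would serve.

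**Conclusion.** The coding rule in SAP section J does not suit the amount-of-information item. Its mean shows the net lean between too little and too much and cannot show how many participants found the amount right. In the assumed examples, a gap of 53.5 points in just right yields a mean difference of zero, and a mean difference of 0.84 fits either a gain or a loss of 34.7 points. Those sizes are illustrative. The defect itself follows from the printed anchors alone.

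The reach is narrow: Exploratory Aim 1c, and Aim 5 only if the item is used there as a linear term. Primary and secondary outcomes are unaffected, and the other three items are properly coded.

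The conclusion assumes that the four 7-point items in Appendix 1 are the section J scale, which their number and format support. It also assumes that no scoring rule exists outside the two documents. Section J refers to survey documents for detail, and the survey printed in the protocol contains no such rule.

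**What to change.** Add to SAP section J, under Information Needs Satisfaction, text to this effect:

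> The amount-of-information item is ideal at 4. It will be reported by arm as too little (1-3), just right (4) and too much (5-7), with the percentage just right as its satisfaction summary. If it enters the Exploratory Aim 5 model, it will enter as these three categories and not as a linear term. The clarity, helpfulness and recommendation items are analysed as continuous, as planned.

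Mean distance from 4 may be added as a supplement. It should not replace the categories, because it discards direction and assumes that the two kinds of complaint are equally bad.

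The cost is a few lines in the SAP and a recode of a variable the survey already collects, plus one extra model parameter if the item is used in Aim 5. The questionnaire, data collection and sample size do not change.

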Research Design. A parallel-arm double-blind RCT of 202 women to evaluate DST (decision support tool) with AS as an option (intervention) vs. DST without AS as an option (control) for a hypothetical diagnosis with low-grade DCIS. The primary outcome is treatment choice (binary: AS vs non-AS). Secondary outcomes include: acceptability of the different treatment options; perceived riskiness of the AS option, and pre- vs post-knowledge about DCIS (self-reported). Using the secure web portal REDCap, eligible consented women will complete three phases: randomization, baseline, and endline. Randomization phase: 1:1 randomization to control (surgery options only) or intervention (surgery options plus active surveillance option) arms, stratified by age group (< 65, 65+) to ensure balance of age-specific mortality risks. Block randomization (k=6) will be used. Baseline phase: all women will receive information about a hypothetical DCIS diagnosis and complete: 1) a baseline questionnaire about breast cancer and DCIS knowledge. Endline phase: after self-directed exploration of provided content, primary and secondary outcomes will be measured by questionnaire. A series of additional covariates and personality scales will also be elicited with the questionnaire. Each woman is expected to take at most one hour to complete the entire study task. In addition to the questionnaire, the team will collect basic website user analytics such as the order in which the website is explored, and how long participants spend on each page. Eligibility. Consented female participants of age 50-79 years, with no history of breast cancer and with a negative mammographic screen within the preceding 12 months. A financial incentive will be provided. Beta-testing. Before roll-out of the RCT, beta-testing of the evaluation will be conducted in 30 women (15 in each trial arm).

Expected Outcomes. An RCT-validated DA that improves understanding of the trade-offs associated with different management strategies for DCIS, and that increases acceptability of AS as a viable management strategy.

Rigor and Transparency. Rigor in DA evaluation is achieved by using a parallel-arm, double-blind randomized controlled trial design. Highest possible robustness and transparency of the approach will be achieved by registering the trial with clinicaltrials.gov and adhering to CONSORT guidelines for analysis.

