Aim R3: Stage 2: Implement an RCT to test the main hypothesis that the use of personalized decision aids leads to (i) an increase in the proportion of women who would consider active surveillance as a viable management strategy for DCIS, and (ii) an increase in knowledge of the associated risk trade-offs.

C. Research Questions

Primary

[figure not shown]
Compared to presenting active monitoring (AM) as an experimental option, does presenting AM as a guideline-concordant care option increase its uptake as treatment choice?

Secondary

Compared to presenting active monitoring (AM) as an experimental option, does presenting active monitoring as a guideline-concordant care option increase AM acceptability, decrease perceived AM riskiness, and decrease uptake of mastectomy as treatment choice?

D. Study Design

Two-arm parallel randomized controlled clinical trial stratified by age (<65 vs. ≥ 65). Block-randomized in both age strata, with block sizes of n=6.

Control: Decision tool with AM:

- AM portrayed as experimental approach currently evaluated in clinical trials
- Contains in-depth information about the 3 surgical options only

Intervention: Decision tool with AM:

- AM offered as standard of care alongside lumpectomy, lumpectomy with radiation, and mastectomy
- Contains in-depth information about all 4 options

Primary data collection with healthy trial participants. All measures, except for participant age, are self-reported. Participants complete a baseline survey prior to randomization (Decision tool with or without AM), use the Decision tool, and then complete a post survey immediately after. The entire session is expected to take less than 1 hour to complete.

E. Sample Size & Randomization

Prior information

- COMET study team poll (n=4): Intervention uptake of AM estimated to be ~15%
- Patient advocate poll (n=10): Intervention uptake of AM estimated to be ~35%

- Currently, <3% of patients do not undergo surgery after diagnosis with DCIS (any type of DCIS)
- Usability testing (much closer to intervention than control version, n=19): uptake ~40%

Targets

- Assume control arm has AM uptake of ~5%
- Difference intervention vs control is thus ~10% (COMET study team) to ~30% (patient advocates)
- Clinically meaningful difference is ~15%
- We want to calculate sample size for $\Delta=15\%$ (control at 5%, intervention at 20%) at significance level $\alpha = 0.05$ and $\geq 90\%$ power

Calculations:

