To answer the primary research question, we will use a log-binomial regression model to test the effect of study arm on binary treatment choice (see primary outcome measure), controlling for age group to account for the stratified design:

$$(1) \quad Y_i = \beta_0 + \beta_1 X_i + \beta_2 a_i$$

where

Y_i = subject i 's response: $Y=1$ for AM, $Y=0$ for non-AM choice

X_i = subject i 's study arm: $X=0$ for control arm, $X=1$ for intervention arm

a_i = subject i 's age group: $a=0$ for age <65 years, $a=1$ for age ≥ 65 years

The main effect of interest (1) is represented by β_1 which quantifies the difference in AM uptake between the two arms and will be reported as $\exp(\beta_1)$ with 95% confidence interval [CI].

To follow the CONSORT statement and because the control arm prevalence is expected to be $>10\%$ we will report risk ratios as the relative measure, and absolute risks in both arms.

K.3. Secondary outcome analyses

Secondary Outcome 1. Linear regression model, as in (1), reported as β_1 (95% CI).

Secondary Outcome 2. Linear regression model, as in (1), reported as β_1 (95% CI).

Secondary Outcome 3. Same analysis as primary outcome analysis, reported as β_1 (95% CI).

Secondary Outcome 4. Linear regression model, controlling for age group, and with random intercepts to account for within-subject dependence.

Model:

$$(1) \quad Y_{ij} = \beta_0 + \beta_1 X_i + \beta_2 t_j + \beta_3 t_j X_i + \beta_4 a_i$$

where

Y_{ij} = subject i 's response at time t_j . (0=surgical; 1=AM)

t_j = time (0=pre-tool; 1=post-tool)

X_i = subject i 's study arm (0 = control; 1 = intervention)

a_i = subject i 's age group: $a=0$ for age <65 years, $a=1$ for age ≥ 65 years

If the models for secondary outcomes 1-4 do not meet the required assumptions for linear models, we will explore using median regression and/or dichotomizing the continuous variable (e.g., top quartile=high, remaining values=normal/low).

K.4. Exploratory aims analyses

Ad hoc statistical analyses will be performed for exploratory aims 1-4. For Exploratory Aim 5 (association of covariates and additional scales with choice), we will extend the model (1) to include covariates and additional scales as outlined sections I and J above. The additional model features will first be assessed for multicollinearity, with features removed if necessary. We will do model building to identify a final model, and present both unadjusted and adjusted parameter estimates for the final model (Table 3).

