	Overall	Intervention	Control	p-value
Demographics				
Age (mean, SD)				
Age group				
<65				
≥ 65				
Sex (Female, N (%))				
Age (mean, SD)				
Race/Ethnicity				
African-American / Black				
American Indian or Alaska Native				
Asian or Pacific Islander				
Hispanic				
White				
Marital Status				
In a relationship				
Married				
Divorced				
Separated				
Single				
Other				
Education				
High school or less				
Some college				
College graduate				
Post-graduate degree				
Rural (N, %)				
Cancer History				
Maximizer Minimizer Scale (mean, SD)				
General pre-tool Knowledge (mean, SD)				
Breast Cancer				
DCIS				
Additional Scales (TBD)				

Table 2. Primary and secondary outcomes at each time point, by treatment arm

	Control	Intervention
Primary Outcome		
Treatment Choice (AM, N, %)		
Secondary Outcomes		
AM Acceptability (mean, SD)		
AM Perceived Risk (mean, SD)		
Mastectomy uptake (N, %)		
Change in self-perceived DCIS knowledge (post-pre, mean, SD)		

Table 3. Intervention Effects on primary and secondary outcomes

	Intervention Effect Overall		Intervention effect: <65 years		Intervention effect: ≥65 years	
Primary Outcome	RR (95%CI)	ARR (95% CI)	RR (95%CI)	ARR (95% CI)	RR (95%CI)	ARR (95% CI)
Choose AM at post-tool						
Risk ratio (95% CI)						
Absolute risk (95% CI)						
	Intervention Effect		Intervention effect: <65 years		Intervention effect: ≥65 years	
Secondary Outcomes	β (95% CI)	aβ (95% CI)	β (95% CI)	aβ (95% CI)	β (95% CI)	aβ (95% CI)
AM Acceptability						
AM Risk						

RR, relative risk; ARR, adjusted relative risk. Adjusted models include [covariate list] as covariates

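### The Secondary Outcome 4 model leaves the pre-tool arm means free; a common pre-tool mean would tighten its estimates by an amount the documents cannot fix (minor efficiency point)

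*SAP*

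**What the plan says.** SAP section K.3 analyses Secondary Outcome 4 by a "Linear regression model, controlling for age group, and with random intercepts to account for within-subject dependence". The model is written as "Y_{ij} = \beta_0 + \beta_1 X_i + \beta_2 t_j + \beta_3 t_j X_i + \beta_4 a_i", where X is arm (1 = intervention), t is time (0 = pre-tool, 1 = post-tool) and a is age group. The pre-tool rating enters as an outcome, not as a covariate.

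The outcome is one 5-point item, treated as continuous. Its hypothesis (SAP section G) is within-arm: "H2.4: In both groups, self-perceived knowledge about DCIS is higher post-tool compared to pre-tool". The protocol's Research Design paragraph also describes it as a pre-versus-post comparison. The completion rule in SAP section E requires both ratings, so every analysed woman has a complete pair.

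The Table 2 shell shows the post-minus-pre change by arm. The Table 3 shell of intervention effects has no knowledge row. K.3 does not say which coefficient will be reported for this outcome. Aim R3(ii) in SAP section B expects the aid to produce "an increase in knowledge of the associated risk trade-offs".

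**The concern.** Both arms rate their knowledge before they see any website content (Protocol, Appendix 1). Under randomisation the expected pre-tool means are therefore equal, and β1 estimates a quantity that is zero by design. Estimating it anyway has two effects. β3 becomes the plain difference in change scores, so a chance gap between arms in the pre-tool ratings passes in full into the contrast and widens its standard error. Each within-arm change is also measured from that arm's own pre-tool mean, although the mean of both arms is a steadier starting point.

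What is at stake is interval width. It matters most if β3 is used as evidence for Aim R3(ii), because this is the only knowledge measure in the SAP with a specified inferential model. The 11-question knowledge scale is descriptive, under Exploratory Aim 1.

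**Working it through.** **The plan's own figures.** The only sizing is for the primary outcome: 101 per arm, 5% versus 20%, 90% power (SAP section E). The normal approximation gives z = (√101 × 0.15 − 1.96 × √(2 × 0.125 × 0.875)) / √(0.05 × 0.95 + 0.20 × 0.80) = (1.507 − 0.917) / 0.456 = 1.297, or 90.3% power. The stated figure reproduces. No power, SD or correlation is stated for Secondary Outcome 4.

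**Inputs.** n = 101 per arm, two time points and complete pairs come from the SAP. The pre-post correlation ρ and the ratio k = s0/s1 (pre-tool SD over post-tool SD) are assumptions, varied below.

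**What β3 is.** Age group enters equally at both times and cancels in the change. With two time points and complete pairs, β3 is the difference between arms in mean raw change. Fitting the planned mixed model to simulated data confirmed this: the two agreed to within 1e-14.

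**Between-arm variance.**
- Planned: (2/n)(s0² + s1² − 2ρ·s0·s1), which equals (2/n)[s1²(1 − ρ²) + (s0 − ρ·s1)²].
- Common pre-tool mean, unstructured covariance: (2/n)·s1²(1 − ρ²), for large samples.
- Proportional reduction: (k − ρ)² / (k² + 1 − 2ρk), which is (1 − ρ)/2 when k = 1.

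**Within-arm variance (H2.4).**
- Planned: (1/n)[s1²(1 − ρ²) + (s0 − ρ·s1)²].
- Common pre-tool mean: (1/n)[s1²(1 − ρ²) + (s0 − ρ·s1)²/2], because the starting mean now rests on 2n women.
- The proportional reduction is half the between-arm one: (1 − ρ)/4 when k = 1.

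**Equal SDs (k = 1), 101 per arm, standard errors in SD units:**

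| ρ | β3 SE, planned | β3 SE, common mean | Variance reduction, β3 | Variance reduction, within-arm |
|---|---|---|---|---|
| 0.2 | 0.178 | 0.138 | 40% | 20% |
| 0.4 | 0.154 | 0.129 | 30% | 15% |
| 0.6 | 0.126 | 0.113 | 20% | 10% |
| 0.8 | 0.089 | 0.084 | 10% | 5% |
| 0.9 | 0.063 | 0.061 | 5% | 2.5% |

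As a check on the β3 column, 4,000 simulated trials at each of ρ = 0.2, 0.4 and 0.6 compared a baseline-adjusted contrast with the change contrast. The variance ratios were 0.57, 0.71 and 0.79, against 0.60, 0.70 and 0.80 from the formula.

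**Unequal SDs, ρ from 0.2 to 0.6, reduction for β3:**
- k = 0.5: 0% to 9% (for example, at ρ = 0.2, 0.3²/1.05 = 8.6%; at ρ = 0.5, exactly 0).
- k = 0.7: 2% to 21% (at ρ = 0.2, 0.5²/1.21 = 20.7%; at ρ = 0.6, 0.1²/0.65 = 1.5%).
- k = 1.25: 40% to 53%.

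If many women start at the bottom of the scale, the correlation may be low, which raises the gain. The same floor can shrink the pre-tool SD, which lowers it. The documents do not show which effect is larger.

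**The case against.** The strongest reply is that the plan does not set out to compare arms on this outcome. H2.4 is within-arm and is tested by β2 (control) and β2 + β3 (intervention), for which the planned model is suitable. The secondary research question in SAP section C lists acceptability, riskiness and mastectomy but not knowledge, and Table 3 leaves knowledge out. Aim R3(ii) concerns risk trade-offs, whereas this item asks how much a woman thinks she knows about DCIS. All of that stands. A reader might infer that the SAP has planned an arm comparison of knowledge and is losing power on it; the documents support neither half, since no arm effect is hypothesised and none is powered. What the reply leaves open is that the same model edit also tightens the two within-arm changes that H2.4 does test.

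A second reply concerns the constraint. Randomisation justifies equal pre-tool means among all women randomised, but the analysed set is completers, and completion is judged partly on what women do after they reach the tool (SAP section E). This is a fair caution and the one real downside. It does not favour the current model: arm-dependent completion would threaten the planned β3 as well.

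A third reply is that an ANCOVA of the post-tool rating would be simpler. It would give the between-arm contrast but would not test H2.4, so it should not replace the repeated-measures model.

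**Conclusion.** The point holds as a minor efficiency suggestion. The planned analysis is valid: under randomisation the change contrast is unbiased, and chance pre-tool imbalance is already reflected in its standard error.

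It is tempting to say that the plan wastes 20% to 40% of the information. That range is only the equal-SD formula at ρ = 0.6 and ρ = 0.2, and the documents give neither the correlation nor the SDs. With equal SDs the reduction in the variance of β3 runs from 5% (ρ = 0.9) to 40% (ρ = 0.2). With a smaller pre-tool SD it may be anywhere from about zero to 20%, and with a larger one it exceeds the equal-SD figure at the same correlation. The within-arm gain is half the between-arm gain throughout. The formulas assume complete pairs, equal allocation, the same covariance in both arms and large samples. The primary analysis is unaffected.

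**What to change.** In K.3, before the data are examined by arm:

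1. Drop β1 from the Secondary Outcome 4 model so that both arms share a pre-tool mean, and replace the random intercept by an unstructured 2×2 covariance. The covariance change is needed because a random intercept forces equal pre- and post-tool variances, so the adjustment would be wrong if the SDs differ.
2. Name the contrasts: β2 and β2 + β3 for H2.4, and β3 with its 95% CI as the between-arm contrast if it is to be used for Aim R3(ii).
3. Read the result beside the pre-tool DCIS knowledge means by arm, already planned for Table 1, and keep the unconstrained model as a check because the analysed set is completers.
4. In the same edit, correct the definition of Y_ij, which codes the response as surgical versus AM although the outcome is a 1-to-5 knowledge rating.

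The cost is a few lines of SAP text and one extra model fit. No new data are needed.
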